6.6. Missing data

For time to event endpoints, a Last Observation Carried Forward & Next Observation Carried Backward statistical approach will be performed to the analysis of longitudinal repeated measures data where some follow-up observations may be missing.

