Medicinal product for Human Use or Investigational Drug	Any substance or combination of substances presented as having properties for treating or preventing disease in human beings or which may be used in or administered to human beings either with a view to restoring, correcting or modifying physiological functions by exerting a pharmacological, immunological or metabolic action, or to making a medical diagnosis (Royal Decree 1090/2015, of 4 December).
Loss of Complete Hematologic Response	Loss of CHR is defined as the appearance of any of the following, confirmed by a second determination ≥ 4 weeks later (unless associated with progression to AP/BC or CML-related death): 
• WBC count that rises to $> 20.0 \times 10^9/L$;• Platelet count that rises to $\geq 600 \times 10^9/L$;

	
• Progressing hepatosplenomegaly to a size \geq 5 cm below the left intercostal margin;• Appearance of \geq 5% myelocytes + metamyelocytes in the peripheral blood;• Appearance of blasts or promyelocytes in the peripheral blood.
Molecular Response (MR)	
• MMR – BCR-ABL \leq 0.1% (IS).• MR4 – BCR-ABL \leq 0.01% (IS).• MR4.5 \leq 0.0032% (IS).• UNDETECTABLE.
Overall Survival (OS)	OS is calculated from the first day of therapy to the date of death. Surviving patients will be censored at the time of the last follow-up.
Subject Number	A unique identifying number assigned to each patient who enrolls (i.e. signs the IC) in the study.
Per-Protocol Set (PPS)	A subset of the full analysis set (FAS) who is compliant with the clinical study protocol (i.e. Composed by subjects that have not incurred in major protocol deviations that could jeopardize the validity of the data and the study outcomes).
Premature Patient Withdrawal	When a subject exits from the study prior to the planned completion of all study treatment administration and/or assessments or procedures. From this time, all study treatment administration is discontinued and no further assessments or procedures will be done, other than the monitoring for progression and/or survival.

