6.1. General features

Principal features of this analysis have been specified in the protocol according to ICH E3 ("Structure and content of clinical study reports") and ICH E9 ("Statistical Principles for Clinical Trials" and addendum Draft R1).

This is a phase Ib/II, single arm, open-label and dose-escalation study designed to determine the safety profile and the recommended phase III dose of bosutinib when administered in combination with atezolizumab in naïve patients with chronic myeloid leukemia in chronic phase.

The investigator should document and explain any deviation from the approved protocol. All significant protocol deviations will be recorded and reported in the Clinical Study Report.

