6.4. Outcome definitions

The primary objective is to evaluate the safety profile of bosutinib 400 mg daily in combination with atezolizumab as first line treatments in participants with chronic myeloid leukemia. The safety set population will be used for all safety analyses. For a detailed description of safety variables analysis see the 6.9 Safety Data Analysis section.

➤ Secondary variables:

- Major Molecular Response (MMR) and Molecular Response (MR) rates at 3, 6, 12 months and at the End of Treatment (EoT) visit.
- Percentage of participants alive at months 6 and 12 and at the EoT visit.
- Number of confirmed MR4 and MR4.5 at end of treatment.
- The rate of confirmed MR4 and MR4.5 at the end of treatment.
- Number of Complete Cytogenetic Responses (CCyR) at 1 year]
- The rate of Complete Cytogenetic Response (CCyR) at 1 year.
- Number of days to response (CCyR, MMR, MR4, MR4.5). [Time Frame: at the EoT visit]
- The median time to response and the overall estimated probability of response (CCyR, MMR, MR4, MR4.5).
- Number of overall surviving patients [Time Frame: at the EoT visit]
- Number of progression-free survival patients.[Time Frame: at the EoT visit]
- Number of failure-free survival patients. [Time Frame at the EoT visit]
- Number of event-free survival patients. [Time Frame: at the EoT visit]
- Immunological Studies: phenotypic Assays:
 - Cell characterization: NK cells (CD3- CD56+; CD16+ CD56+; TNF α ; IFN α ; Granzyme b NK-LGL cells (CD56+ CD57+), T-LGL cells (CD3+ CD57+), CD8 TCR α/β , NK markers (NKG2D, KIR2DL2/DL3/DS2, KIR2DL5B).
 - b. Differentiation and maturation (NKG2A/CD16) and proliferation (NK67) markers of NK cells.

- c. CD4+ T cells activation markers: CD25 CD69 HLA-DR.
- d. Predictive markers of CML relapse: T regs (CD4+ CD25int-hi CD127low), CD8+ T cells (PD-1/PD-L1) and plasmacytoid dendritic cells (CD86+).

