6.5. Analysis methods

Descriptive statistics are presented using mean and standard deviations for continuous variables and count and percentages for categorical variables. The 95% confidence interval (CI) for a proportion will be reported for the primary efficacy variable. The Shapiro-Wilks test will be used to test the normality of the distribution of continuous variables. Statistical differences between groups were analyzed using the chi-square test for categorical data and the Student's t test for quantitative data. Quantitative data showing non-normal distribution were analyzed using the Mann-Whitney U test. The Kaplan-Meier method is used to study survival. A p-value of <0.05 was considered statistically significant. All analyses were carried out with the free statistical program R (<https://cran.r-project.org/>).

Primary Objective:

Frequency and percentage of adverse events will be summarized by system organ class and/or preferred term, severity (based on CTCAE grades), type of adverse event and causality relation to study treatment by the study phases. 95% confidence intervals of the proportion of adverse events will be computed using the exact binomial distribution.

Secondary Objectives: The rates of molecular responses at certain time points as well as the percentages will be presented together with an exact 95% binomial confidence interval.

All time to event endpoints will be analyzed using the Kaplan-Meier method and will be presented by Kaplan-Meier method plots.

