6.7. Sensitivity analysis

A sensitivity analysis employing only participants with complete data will be performed in order to demonstrate that study conclusions are invariant to assumptions, the particular model, and methods of handling missing data.

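### SAP 6.6 fills time-to-event data by LOCF and NOCB instead of censoring, so dropouts can count as non-responders to EoT and response dates across a missed sample are ambiguous

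*SAP*

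**What the plan says.** The whole missing-data section of the SAP (6.6) is one sentence. It opens "For time to event endpoints, a Last Observation Carried Forward & Next Observation Carried Backward statistical approach will be performed" and continues "to the analysis of longitudinal repeated measures data where some follow-up observations may be missing". It gives no order for the two fills, no limit on the gap, and no rule for what happens after a patient's last sample.

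SAP 6.5 says "All time to event endpoints will be analyzed using the Kaplan-Meier method and will be presented by Kaplan-Meier method plots". SAP 6.4 lists among the secondary variables "Number of days to response (CCyR, MMR, MR4, MR4.5). [Time Frame: at the EoT visit", followed by the median time to response and the overall estimated probability of response.

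Censoring rules exist elsewhere, but only for survival endpoints. Protocol section 4 says of overall survival that "Surviving patients will be censored at the time of the last follow-up", and it censors progression-free survival at the last hematological assessment. The SAP leans on the Protocol for such matters: "Principal features of this analysis have been specified in the protocol according to ICH E3". For time to response, neither document states a date of event or a date of censoring.

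SAP 6.7 adds: "A sensitivity analysis employing only participants with complete data will be performed in order to demonstrate that study conclusions are invariant to assumptions". The same sentence extends that claim to the handling of missing data.

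**The concern.** Kaplan-Meier deals with incomplete follow-up by censoring: a patient stops contributing at the last time the status was known. LOCF puts a known status in place of an unknown one. A patient who leaves the study without a response keeps a negative value at every later visit, stays in the risk set to EoT, and is counted as never having responded. Protocol section 4 says that after premature withdrawal only progression and survival are still monitored, so the BCR-ABL series does stop there. Protocol 9.5 and 11.6 give several routes to withdrawal, so this is not a remote case.

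The second problem lies inside the series. When a sample is missed between a negative and a positive one, LOCF makes the missed visit negative and NOCB makes it positive. Two analysts following SAP 6.6 could date the same patient's response to different visits, one of them a visit at which nothing was measured.

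At stake are the days to response, the median time to response and the estimated probability of response.

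**Working it through.** **Sampling days.** Protocol 12.14 places post-baseline BCR-ABL samples on day 1 of cycles 2, 4, 7, 10, 13, 17, 20 and 23, and at EoT. With study day = 28 × (cycle − 1) + day in cycle, these are D29, 85, 169, 253, 337, 449, 533 and 617, exactly as in Tables 14 to 17. EoT (cycle 25, day 29) computes to D701 and is tabulated as D700; D700 is used here. There is no BCR-ABL sample at D365.

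**Response model (assumed).** Protocol 6.2 reports 116 of 246 bosutinib patients in MMR after one year. I take an exponential time to MMR with that proportion placed at D337: λ = −ln(1 − 116/246)/337 = 0.001893 per day. True probability by D700 = 1 − exp(−0.001893 × 700) = 73.4%.

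**(a) LOCF past the last sample.** If every non-responder is carried to EoT, nobody is censored, and the Kaplan-Meier value at D700 is simply the share of patients with an observed positive sample. Let w be the probability that onset falls in the interval ending at a sample, and G the probability of still being in the study at that sample. With an assumed 20% dropout by D700 at a constant rate, independent of response, G = 0.8^(day/700).

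| Day | w | G | w × G |
|---|---|---|---|
| 29 | 0.0534 | 0.9908 | 0.0529 |
| 85 | 0.0952 | 0.9733 | 0.0927 |
| 169 | 0.1251 | 0.9476 | 0.1185 |
| 253 | 0.1067 | 0.9225 | 0.0984 |
| 337 | 0.0911 | 0.8981 | 0.0818 |
| 449 | 0.1009 | 0.8666 | 0.0874 |
| 533 | 0.0628 | 0.8437 | 0.0530 |
| 617 | 0.0536 | 0.8214 | 0.0440 |
| 700 | 0.0452 | 0.8000 | 0.0362 |
| Sum | 0.734 | | 0.665 |

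With each sample also missed independently with probability p, the sum becomes Σ w_j Σ_{k≥j} p^(k−j)(1 − p) G_k. At p = 5%:

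- no dropout: 0.7341 − 0.0452 × 0.05 − 0.0536 × 0.05² = 73.2%
- 10% dropout: 69.8%
- 20% dropout: 66.2%
- 30% dropout: 62.5%

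Simulation of the same model with non-responders censored at their last observed sample gives about 73.5% both with no dropout and with 20% dropout. At 20% dropout the LOCF shortfall is therefore 73.4 − 66.2 = 7.2 points, or 0.072 × 31 = 2.2 responders among 31 patients. The standard error at n = 31 is √(0.734 × 0.266/31) = 7.9 points.

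**(b) Order of the fills.** For one missed sample with a negative before and a positive after, LOCF first dates the response to the actual positive sample (shift 0). NOCB first dates it to the missed visit, so the shift is the gap between the two days:

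- D29 missed: 85 − 29 = 56 days
- D85, D169, D253, D449 or D533 missed: 84 days
- D337 missed: 449 − 337 = 112 days
- D617 missed: 700 − 617 = 83 days

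Two consecutive misses give 140 to 196 days. For CCyR the marrow schedule of Tables 14 and 15 includes D365, so the shortest shift is 365 − 337 = 28 days.

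**Effect of the order at EoT.** In simulation, with non-responders censored at the last sample and 5/10/20/30% of samples missed, D700 response is 73.43/73.36/73.23/73.02% with NOCB first and 73.46/73.45/73.65/74.12% with dating at the first actual positive sample: differences of 0.0/0.1/0.4/1.1 points. The median visit stays at D449 except with NOCB first at 30% missed, where it becomes D337.

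**SAP 6.7.** Patients with complete data have no gaps, so neither fill acts on them. If complete means all nine post-baseline samples, (1 − p)^9 = 63/39/13/4% of patients qualify at 5/10/20/30% missed. Agreement or disagreement with that subset says nothing about how the fills behave.

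**The case against.** The sentence in SAP 6.6 speaks of repeated measures with some missing observations. It can be read as a rule for intermittent gaps only, with censoring left to Kaplan-Meier. It names LOCF before NOCB, and in that order the response falls on the first actual positive sample, with no shift. That reading is reasonable, but the SAP does not state it, and it leaves NOCB with nothing to do: every patient is scheduled for a screening sample, so LOCF fills every later gap first. Nor does it supply the missing censoring date.

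The size in (a) depends on an assumed dropout rate, and the analysis set could shrink it. The FAS consists of patients who completed the combination cycles, and Protocol 11.6 ties the efficacy analysis to the per-protocol set. If time to response is run in either set, early dropouts are already excluded, only later dropout matters, and fewer than 31 patients remain. This stands as a limit on the size, not on the defect.

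Three stronger inferences are tempting and do not hold. A reader might conclude that the 12-month MMR rate is distorted; SAP 6.5 reports rates at fixed times with exact binomial intervals, and SAP 6.6 confines the fills to time-to-event endpoints. A reader might conclude that OS and PFS lack censoring rules; Protocol section 4 has them. And a reader might take 56 to 112 days as a general error; it applies only with NOCB first, one missed BCR-ABL sample and nominal visit days.

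**Conclusion.** The concern holds as a specification defect in secondary, descriptive endpoints. The primary safety objective, the landmark MMR rates and the OS and PFS censoring rules are not affected.

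The more important part is (a). Literal LOCF biases the estimated probability of response downward, by about 0.2 points with no dropout and about 7 points with 20% dropout at 5% missed samples, slightly less than one standard error at n = 31. This rests on the exponential model, on dropout unrelated to response, and on assumed dropout and missed-sample rates; the documents give neither rate. Part (b) mainly makes individual response dates irreproducible. It moves the EoT probability by about 0 to 1 point and rarely the median visit. If LOCF is carried to EoT under either order, the order makes no difference at D700, because the same patients respond and nobody is censored.

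The complete-data analysis in SAP 6.7 cannot serve as the safeguard it is said to be.

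**What to change.** In SAP 6.6, remove LOCF and NOCB for time-to-event endpoints. State that a response is dated at the first actual sample that meets the definition, and that patients without a response are censored at their last evaluable BCR-ABL sample, or cytogenetic sample for CCyR. State that OS and PFS follow the censoring rules in Protocol section 4.

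In SAP 6.7, define complete data and describe the analysis as a comparison with that subset, without saying that it demonstrates invariance to missing-data handling.

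The cost is SAP wording only: no new visits, samples or patients. The drawback is that dating at actual samples errs slightly late when a visit is missed. In the simulation without dropout, the Kaplan-Meier curve read at D337 (not a listed endpoint) is 0.5 to 4.1 points low at 5 to 30% missed. The gain is that every date rests on a real sample and every analyst obtains the same one. An interval-censored (Turnbull) estimate of time to response could be added as a sensitivity analysis, but is optional. Failure-free and event-free survival also lack definitions; that is a separate matter.

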6.7. Sensitivity analysis

A sensitivity analysis employing only participants with complete data will be performed in order to demonstrate that study conclusions are invariant to assumptions, the particular model, and methods of handling missing data.

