4 DEFINITION OF TERMS

Assessment	A procedure used to generate data required by the study.
Accelerated Phase (AP)	
• $\geq 15\%$ blasts in the peripheral blood or bone marrow aspirate, but $< 30\%$ blasts in both the peripheral blood and bone marrow aspirate;• $\geq 30\%$ blasts plus promyelocytes in peripheral blood or bone marrow aspirate;• $\geq 20\%$ basophils in the peripheral blood;• Thrombocytopenia ($<100 \times 10^9/L$) that is unrelated to therapy.
Blast Crisis (BC)	$\geq 30\%$ blasts in peripheral blood or bone marrow aspirate Appearance of extra medullary involvement other than hepatosplenomegaly proven by biopsy (i.e., chloroma).
Complete Hematologic Response (CHR)	
• Complete normalization of peripheral blood counts with leukocyte count $<10 \times 10^9/L$• Platelet count $<450 \times 10^9/L$• No immature cells, such as myelocytes, promyelocytes, or blasts in peripheral blood• No signs and symptoms of disease with disappearance of palpable splenomegaly
Complete Molecular Response (CMR)	Undetectable BCR-ABL levels with high sample sensitivity (10^{-5} or greater) for a minimum of 2 years.
Cytogenetic Response (CyR)	
• Complete (CCyR): 0% Ph+ metaphases.• Partial (PCyR): > 0 to 35% Ph+ metaphases.• Minor (mCyR): >35 to 65% Ph+ metaphases.• Minimal: >65 to 95% Ph+ metaphases.• None: > 95 to 100% Ph+ metaphases.
Cycle of treatment	28 days of treatment
Disease Progression	The following events are considered disease progression: 
• AP.• BC.• CML-related death.
Enrollment	It is the time until all patients are included in the study, i.e. all patients received at least one dose of study medication. Previously they must have signed an informed consent (i.e., prior to starting any of the procedures described in the protocol).
Full Analysis Set (FAS)	The full analysis set (FAS) comprises all patients who complete the treatment with bosutinib in combination with atezolizumab for 12 cycles successfully.

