11.6 Dose Modification and Dose Delay

The following section summarizes dosing modifications of bosutinib or atezolizumab to manage possible toxicity. Administration of bosutinib or atezolizumab could be stopped for an individual subject in the event of a treatment-related toxicity that, in the Investigator's assessment, warrants discontinuation. Exceptions to these guidelines will require approval from the Medical Monitor.

A maximum discontinuation of 1 month is allowed for the treatment with bosutinib if required due to the onset of adverse events, investigator decision, or other major circumstances. If a subject discontinued treatment for more than one month he/she will be withdrawn from the study and the appropriate follow-up procedures will be conducted. Also, to be included in the

efficacy analysis (Per protocol set population), a subject must comply with at least 70% of treatment with bosutinib. Regarding atezolizumab treatment, fail to administrate up to 3 out of the 11 administrations scheduled, will be allowed to continue in the study. If, for any reason, atezolizumab could not be administered 4 or more times during the course of the study, the subject will be withdrawn from the study and the appropriate follow-up procedures will be conducted. All deviations from the scheduled treatments regime shall be recorded in the patients' clinical history and the eCRF and explained if required.

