5.3. Withdrawal/follow-up

Patients may suspend their participation in the study whenever they wish, based on his/her own judgement and opinion, without giving any explanation, although the investigator may investigate the reasons of a voluntary dropout.

The investigator may also decide to withdraw a patient from the trial if he/she does not comply with the protocol, due to AEs or treatment inefficacy or toxicity.

Patients who do not comply with at least 70% of the scheduled doses of bosutinib or that, in 4 or more times, the administration of atezolizumab is cancelled, will be withdrawn from the study.

6. Statistical Principles

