6.2. Analysis Populations

All data will be received from the sponsor duly anonymized. All analyzes carried out and results of software applications will be duly dated and stored.

Full Analysis Set: The full analysis set (FAS) comprises all patients who complete the first three phases of treatment (combination of bosutinib and atezolizumab) successfully.

Safety Set: The safety set (SS) includes all patients who received at least one dose of study medication. Reporting and analysis of safety information for these patients will be split into subsets by study phases.

Per-Protocol Set: The per-protocol set (PPS) consists of a subset of the patients in the FAS who are compliant with requirements of the clinical study protocol (CSP). A compliance of 70% with bosutinib treatment will be necessary to be included in the PPS. Protocol deviations leading to exclusion from the PPS will be detailed in the Clinical Study Report.

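### The SAP's only sensitivity analysis, a complete-case rerun, cannot demonstrate invariance to missing-data assumptions, least of all when early leavers are already outside the full analysis set

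*SAP*

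**What the plan says.** SAP 6.7 names a single sensitivity analysis and states its purpose: "A sensitivity analysis employing only participants with complete data will be performed in order to demonstrate that study conclusions are invariant to assumptions". The sentence goes on to include "the particular model, and methods of handling missing data".

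The method it would be set against is in SAP 6.6: "For time to event endpoints, a Last Observation Carried Forward & Next Observation Carried Backward statistical approach will be performed". That rule is introduced for time-to-event endpoints but described in terms of repeated measures, so its application to response rates is not clear. Neither document plans a non-responder analysis, best- and worst-case bounds, or any other analysis allowing dropout to depend on the unseen outcome. Protocol section 15 has no part on missing data.

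The analysis sets matter here. SAP 6.2 says: "The full analysis set (FAS) comprises all patients who complete the first three phases of treatment (combination of bosutinib and atezolizumab) successfully". Protocol section 4 gives the same set as one that "comprises all patients who complete the treatment with bosutinib in combination with atezolizumab for 12 cycles successfully". The per-protocol set lies inside it: "The per-protocol set (PPS) consists of a subset of the patients in the FAS who are compliant". Protocol 11.6 identifies the per-protocol set with the efficacy analysis, for which "a subject must comply with at least 70% of treatment with bosutinib".

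On leaving the study, SAP 5.3 lets the investigator withdraw a patient for non-compliance and also "due to AEs or treatment inefficacy or toxicity". Under Protocol section 4 (premature patient withdrawal), only progression and survival are followed after that.

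**The concern.** A complete-case analysis is itself a missing-data assumption, and a demanding one: that patients without values resemble patients with them. Here that is doubtful. Toxicity and lack of effect are listed reasons for withdrawal, and the scheduled BCR-ABL and cytogenetic values that would have followed are not collected. The patients whose outcomes are in doubt are therefore the ones the rerun sets aside.

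The stated purpose also presupposes its result: it is to demonstrate invariance, where a sensitivity analysis should assess it. If the two analyses agree, a report following the SAP's wording would have grounds to call the molecular and cytogenetic response rates robust to missing data, although neither analysis had examined the early leavers. These rates bear on the trial's rationale, which is that the combination should raise molecular response.

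**Working it through.** **1. The plan's own figure.** Protocol 15.5 and SAP 4.3 take 36 patients and a loss of at most 15% before the combination: 36 × (1 − 0.15) = 30.6, which reproduces the stated 30-31. There is no power calculation to reproduce.

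**2. What the rerun changes.**

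- Assumption about missing values: changed from carry-forward/backward (if applied to the endpoint) to leavers being like stayers.
- Model: unchanged.
- Dropout that depends on the unseen outcome: not examined.

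**3. Who is in each analysis, by time point.** Protocol 12.1 equates one month with one 28-day cycle. BCR-ABL is sampled on day 1 of cycles 4, 7 and 13 (Protocol 12.14), that is, after 3, 6 and 12 cycles. The 12 combination cycles are cycles 2 to 13. Anyone in the full analysis set was therefore still on study at all three samples, and anyone who left earlier is outside both analyses. Only isolated missed samples can separate the two.

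End of treatment comes 12 monotherapy cycles later, so patients in the set can be lost in between. Assumed example, with carry-forward applied to rates: 26 in the set, 4 without an end-of-treatment value, carry-forward 13/26 = 50%.

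- All four carried forward as non-responders: complete-case 13/22 = 59%.
- All four carried forward as responders: complete-case (13 − 4)/22 = 9/22 = 41%.

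The analyses differ, but only through values already observed.

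**4. Size of what is left unexamined.** The documents give no dropout rate after the combination starts, so these counts are assumptions: 36 treated, 5 lost before the combination (0.15 × 36 = 5.4), 5 lost later, 26 completers, 13 responders. Exact (Clopper-Pearson) 95% intervals:

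- Complete-case: 13/26 = 50% (30-70).
- All treated, missing = non-response: 13/36 = 36% (21-54).
- All treated, missing = response: (13 + 10)/36 = 23/36 = 64% (46-79).
- The 31 who start the combination: 13/31 = 42% to (13 + 5)/31 = 18/31 = 58%.

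The bounds are 10/36 = 28 points apart over all treated patients and 5/31 = 16 points apart among those who start the combination.

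**5. Range over the unknown dropout.** Here 30 or 31 start the combination, and responders are the whole number nearest 116/246 (47%, the 12-month bosutinib rate in Protocol 6.2) of completers.

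| Later losses | Completers | Complete-case | Lower bound over 36 | Upper bound over 36 |
|---|---|---|---|---|
| 0 | 30-31 | 46.7-48.4% | 38.9-41.7% | 55.6% |
| 3 | 27-28 | 46.4-48.1% | 36.1% | 58.3-61.1% |
| 6 | 24-25 | 45.8-48.0% | 30.6-33.3% | 63.9% |
| 9 | 21-22 | 45.5-47.6% | 27.8% | 66.7-69.4% |

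The complete-case column is steady because the completer rate was fixed by assumption. The informative part is the widening of the bounds, which a complete-case rerun cannot show.

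**The case against.** Several points on the other side stand.

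- The rerun is not empty. It replaces the carry-forward assumption of SAP 6.6 with a different one, so it is a weak alternative and not the absence of one.
- A reader might infer that the main and sensitivity analyses must always agree. The documents do not support that: as step 3 shows, they can differ at end of treatment. Near-agreement is to be expected mainly at 3, 6 and 12 months.
- A reader might take 28 points as the true uncertainty. It is the distance between extreme bounds on assumed counts. The upper bound over all 36 counts as responders five patients who left after one bosutinib cycle without receiving atezolizumab. All ten missing patients in the illustration are outside the full analysis set, so the width comes chiefly from that set's definition. The fault of SAP 6.7 is that it cannot reveal it.
- A reader might infer that robustness will be claimed whatever happens. Nothing in SAP 6.7 forbids reporting a difference; a misleading claim is a risk that follows from the stated purpose.
- Survival and progression are less exposed. Withdrawn patients are still followed for both, Protocol section 4 gives censoring rules, and the early-termination visit in Protocol 12.20 collects disease status.

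None of this gives the rerun the property that the SAP assigns to it.

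**Conclusion.** The point holds as a defect in the stated purpose and content of SAP 6.7. A complete-case rerun cannot demonstrate invariance to assumptions, model or missing-data method, and it cannot address dropout related to outcome, which the withdrawal rules make plausible. At 3, 6 and 12 months its agreement with the main analysis would say little about the early leavers.

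The reach is limited. The primary objective is safety, analysed in all dosed patients (SAP 6.4), and is untouched. The effect falls on the secondary molecular and cytogenetic response rates of a study that calls itself exploratory.

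The size depends on dropout that the documents do not give. With the assumed counts, a complete-case 50% sits between bounds of 36% and 64% over all treated patients, or 42% and 58% over those who start the combination. The conclusion also assumes that efficacy is analysed in the full or per-protocol set, as Protocol 11.6 indicates; SAP 6.5 does not name the set.

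**What to change.** In SAP 6.7:

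- Restate the aim as assessing the robustness of the conclusions, in place of demonstrating that they are invariant.
- For each molecular and cytogenetic response rate, add an analysis over all treated patients, and another over all who start the combination, counting missing as non-response.
- Show missing counted as response beside it, labelled as an extreme bound.
- Keep the complete-case result as descriptive.

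A tipping-point count is not proposed, because no response endpoint has a stated success criterion to tip.

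The cost is a wording change and a few extra table columns, with no new data or visits. The reported response rates will look less favourable.
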